12.6 Secondary Endpoints

12.6.1 *Secondary Safety Endpoint*

- Assessment of the safety and tolerability of PLN-74809 in IPF participants

Safety data from all participants who received at least one dose of study drug will be incorporated into the final safety analysis. Further details of the safety analyses will be provided in the SAP. AEs will be collected from the time the participant signs the ICF until the last study visit. Treatment-emergent adverse events (TEAEs) are defined as AEs that emerged or worsened in severity after the first administration of study drug.

AEs will be coded using the Medical Dictionary for Regulatory Activities (MedDRA®). All AEs will be graded for severity per the CTCAE grading scale and listed by participant and summarized by treatment.

The incidence of AEs, the incidence of TEAEs, the incidence of treatment-related AEs, and the severity of AEs will be summarized by system organ class, preferred term, and maximum severity. In cases where a participant reports multiple occurrences of the same event (preferred term), the greatest severity will be included in the summary. The number and percentage of participants with SAEs and treatment-related SAEs, and the number and percentage of participants who withdraw due to an AE will be tabulated by study treatment and dose.

Clinical laboratory test parameters will be listed, using the CTCAE grading scale, for individual participants, with values outside the reference ranges flagged. The incidence of treatment-emergent laboratory abnormalities will be summarized by severity. Summary statistics will be calculated for each parameter.

Individual ECG results will be listed for each participant. Summaries of ECGs will include changes from baseline for each parameter. The number and percentage of participants with abnormal ECGs will be summarized by treatment.

Vital sign measurements other laboratory tests, concomitant medications, medical history and changes in physical examinations at each time point will be listed by participant.

Concomitant medications will be coded using the most current World Health Organization drug dictionary available.

12.7 Exploratory Endpoints

12.7.1 Exploratory Pharmacodynamic/Pharmacokinetic Endpoints

- Relationship between PLN-74809 systemic exposure and PET imaging and biomarkers in IPF participants

Pharmacokinetics

Plasma PLN-74809 concentrations at each sampling time point will be presented in listings and summarized with descriptive statistics. Plasma PLN-74809-versus-time profiles (with plasma concentrations on both a log and linear scale) will be plotted for each participant. Non-compartmental analysis will be used to calculate PK parameters as appropriate. Plasma PK parameters will be presented in listings and summarized with descriptive statistics. The data will also be presented graphically.

Further details of the analyses will be provided in the SAP to be prepared and agreed prior to final ‘database lock’ at the end of the study. The PK analysis plan and report may be prepared separately from the SAP as appropriate.

PET/MRI

Relationships between PK and type 1 collagen deposition, as well as between MRI and PET imaging, may be evaluated in an exploratory fashion and presented in a graphical manner. The analysis of PET/MRI imaging is described in [Section 12.5.1](#).

Pharmacodynamics: Biomarkers

Urine, plasma, and serum samples will be analyzed for biomarkers (presence or actual concentration). These samples will be used to determine the levels of these markers in participants, the relationship between these markers, and the level of PET tracer uptake (type 1 collagen deposition) in the lung. Results will be presented in listings and summarized with descriptive statistics and in graphical form.

12.7.2 Exploratory Efficacy Endpoints

12.7.2.1 Forced Vital Capacity (FVC)

- Absolute FVC volume and FVC as percent of predicted as assessed by spirometry

Percent of predicted FVC and volume (mL) will be assessed using the standard spirometry procedure at the Chest Clinic at Massachusetts General Hospital and presented as absolute

values and as percent of predicted values. Baseline FVC will be the average of the screening and Day 1 determinations. End-of-study FVC will be the average of Week 12 and Week 14 determinations.

12.7.2.2 Patient-reported Outcome (PRO)

- Patient-reported outcome (PRO): a VAS for cough severity

A cough VAS will be completed at the timepoints specified in the Schedule of Events ([Appendix 1](#)).

12.8 **Other Assessments or Analyses**

Unbound concentrations of PLN-74809 will be determined in plasma samples. Exploratory metabolite evaluation may be performed in plasma samples.

12.9 **Interim Analysis**

Not applicable

13 QUALITY CONTROL AND ASSURANCE

During the study, the Sponsor and/or representatives of the Sponsor may visit the site to conduct an audit of the study. The purpose of this visit will be to determine the Investigator's adherence to the protocol, applicable regulations, and the Sponsor procedures, in addition to assessing the accuracy of the study data. Prior to initiating this audit, the Investigator will be contacted by the Sponsor to arrange a convenient time for this visit. The Investigator and staff are expected to cooperate with the auditors and allow access to all participant records supporting the eCRFs and other study-related documents.

At some point during the development program for the study drug, a regulatory authority may visit the Investigator to conduct an inspection of the study and the site. The Investigator and staff are expected to cooperate with the inspectors and allow access to all source documents supporting the eCRFs and other study related documents. The Investigator must immediately notify the Sponsor when contacted by any regulatory authority for purposes of conducting an inspection.

14 ADMINISTRATIVE CONSIDERATIONS

14.1 Institutional Review Board, Independent Ethics Committee or Research Ethics Board Approval

The Investigator must inform and obtain approval from the IRB/IEC/REB for the conduct of the study at named sites, for the protocol, the participant ICF, and any other written information that will be provided to the participants and any advertisements that will be used. Written approval must be obtained prior to recruitment of participants into the study and shipment of investigational agent.

Proposed amendments to the protocol and aforementioned documents must be discussed between the Sponsor and contract research organization (CRO), and then submitted to the IRB/IEC/REB for approval as well as submitted to regulatory authorities for approval prior to implementation. Amendments may be implemented only after a copy of the local IRB/IEC/REB approval letter has been transmitted to the Sponsor. Amendments that are intended to eliminate an apparent immediate hazard to participants may be implemented prior to receiving Sponsor or IRB/IEC/REB approval. However, in this case, approval must be obtained as soon as possible after implementation.

The Investigator is responsible for reporting protocol deviations to the IRB/IEC/REB as required by local requirements. The Investigator will be responsible for ensuring that an annual update is sent to the IRB/IEC/REB to facilitate their continuing review of the trial (if needed) and that the IRB/IEC/REB is informed about the end of the study. Copies of the update, subsequent approvals and final letter must be sent to the Sponsor.

14.2 Ethical Conduct of the Study

The study will be carried out in accordance with the current version of the Declaration of Helsinki, concerning medical research in humans. The study will be conducted in adherence to the study protocol and Good Clinical Practice (GCP), as defined in Title 21 of the US Code of Federal Regulations Parts 50, 54 56, 312 and Part 11 as well as International Council on Harmonisation (ICH) E6: Guideline for Good Clinical Practice (ICH GCP) consolidated guidelines (E6) and applicable regulatory requirements.

14.3 Participant Information and Consent

It is the Investigator's responsibility to obtain written informed consent from the participant after adequate explanation of the objectives, methods, anticipated benefits, and potential hazards of the study and before any study procedures are commenced.

The participant should be given a copy of the IRB/IEC/REB-approved ICF in his/her native language. The informed consent process should be recorded in the source documentation. The original copy of the signed and dated ICF must be retained in the institution's records and be available for inspection by representatives of the Sponsor, or representatives from regulatory agencies. The participant will be given a copy of the signed ICF.

Participants unable to sign the ICF may participate in the study if a legal representative or witness provides the consent (in accordance with the procedures of ICH-GCP and local regulations) and the participant confirms his/her interest in study participation.

The participant will be informed that he/she can freely withdraw consent and stop participation in the study at any time with no prejudice to further treatment. It is the participant's responsibility to communicate this decision to the Investigator.

14.4 Participant Confidentiality

The Investigator must ensure that the participant's privacy is maintained. On the CRF and other documents submitted to the Sponsor, participants will be identified by a participant study number only. Documents that are not submitted to the Sponsor (eg, signed ICF) should be kept in a strictly confidential file by the Investigator.

The Investigator shall permit authorized representatives of the Sponsor, regulatory agencies, and IRBs/IECs/REBs to review the portion of the participant's medical record that is directly related to the study. As part of the required content of informed consent, the participant must be informed that his/her records will be reviewed in this manner.

Applicable data privacy laws and regulations must be adhered to. The Investigator and the Sponsor are responsible for ensuring that sensitive information is handled in accordance with local requirements (eg, Health Insurance Portability and Accountability Act [HIPAA], Personnel Information Protection and Electronic Documents Act [PIPEDA], General Data Protection Regulation [GDPR]). Appropriate consent and authorizations for use and disclosure and/or transfer (if applicable) of protected information must be obtained.

14.5 Study Monitoring

The Investigator must allow the Study Monitors to periodically review, at mutually convenient times, during the study and after the study has been completed, all eCRFs and office, hospital, and laboratory records supporting the participation of each participant in the study. The eCRFs and other documentation supporting the study must be kept up to date by the Investigator and the research staff at the investigative site. These study materials must be available for review by the Study Monitor, and/or other qualified representatives of the Sponsor, at each monitoring visit.

It is the monitor's responsibility to inspect the CRFs at regular intervals throughout the trial to verify adherence to the protocol, the completeness, accuracy and consistency of the data, and adherence to GCP guidelines.

The Investigator agrees to cooperate with the monitor to ensure that any problems detected during the course of these monitoring visits are resolved.

14.6 Case Report Forms and Study Records

The investigative site will use eCRFs to record all the protocol-specified data for each participant enrolled in this study. Entries made in the eCRF must be verifiable against source documents. Data reported in the eCRF that are derived from source documents should be consistent with the source documents or the discrepancies should be explained.

The Investigator will be responsible for reviewing all data and eCRF entries and will sign and date the designated pages in each participant's eCRF, verifying that the information is accurate.

14.7 Adjudication Committee

Potential acute exacerbations, respiratory-related hospitalizations, and/or respiratory-related deaths will be reviewed by an adjudication committee.

14.8 Retention of Data

The Investigator must ensure that all records pertaining to the conduct of the clinical study, ICFs, drug accountability records, source documents, and other study documentation are adequately maintained for a period of 2 years after the last approval of a marketing application in an ICH region and until there are no pending or contemplated marketing applications in an ICH region or at least 2 years have elapsed since the formal discontinuation of clinical development of the study drug.

The Investigator must not destroy any records associated with the study without receiving approval from the Sponsor. The Investigator must notify the Sponsor in the event of accidental loss or destruction of any study records.

Whenever possible, an original recording of an observation must be retained as the source document. However, a photocopy of a record is acceptable provided it is legible and is a verified copy of the original document.

All eCRF data entered by the site (including audit trail), as well as computer hardware and software (for accessing the data), will be maintained or made available at the site in compliance with applicable record retention regulations. The CRO will retain the original eCRF data and audit trail.

14.9 Financial Disclosure

Financial Disclosure statements will be handled in a separate agreement apart from the protocol, kept on file, and submitted as applicable with any subsequent license application.

14.10 Publication and Disclosure Policy

The data generated in this clinical study are the exclusive property of the Sponsor and are confidential. Any publication of the results of this study must be authorized by the Sponsor. The Sponsor will have the opportunity to review any publications that arise from the

Investigators before submission for publication. Any such review and approval of publications related to the study shall be made pursuant to the process agreed between the parties in the site's clinical trial agreement with Sponsor. Authorship on any publication of the results from this study will be based on contributions to study design, data acquisition and analysis, and interpretation of results.

APPENDIX 1 SCHEDULE OF EVENTS

	Screening		Treatment						EoS / ET
	Visit 1	Visit 2	Visit 3	Visit 4	Visit 5	Visit 6	Visit 7 ^a	Visit 8 ^a	
	Day -28 to Day -1	Pre- Baseline Day -7 to Day -1	Baseline Day 1	Week 2 Day 14 (±2 days)	Week 4 Day 28 (±2 days)	Week 8 Day 56 (±3 days)	Day 84 (-7days)	Week 12 Day 84 (±3 days)	Week 14 Day 98 (±3 days)
Informed consent	X								
Medical history	X								
Demographics (age, sex, race)	X								
Serum pregnancy test	X								
Check inclusion and exclusion criteria	X		X						
Complete physical examination (including height and weight)	X								
Targeted physical examination			X	X	X	X		X	X
Randomization			X						
FVC ^{b,c}	X		X		X	X		X	X
FEV1 ^c	X								
DLco	X								
Cough VAS	X		X	X	X	X		X	X
Vital signs (post 3 minutes, supine; approx 2 hours post dose and around the time of the ECG)	X		X	X	X	X		X	X
Tripple 12-lead ECG (post 10 minutes, supine; at least 2 hours post dose and prior to the PK sample) ^{d,e}	X		X	X	X	X		X	X
Hematology (post 8-hour fast)	X		X	X	X	X		X	X
Clinical chemistry (post 8-hour fast) ^f	X		X	X	X	X		X	X
Coagulation (post 8-hour fast)	X		X	X	X	X		X	X
PET/MRI scan		X						X	
Pharmacokinetic sample plasma ^g			X		X			X	X ^{e,f,h}

	Screening	Treatment								EoS / ET
	Visit 1	Visit 2	Visit 3	Visit 4	Visit 5	Visit 6	Visit 7 ^a	Visit 8 ^a	Visit 9	
	Day -28 to Day -1	Pre-Baseline Day -7 to Day -1	Baseline Day 1	Week 2 Day 14 (±2 days)	Week 4 Day 28 (±2 days)	Week 8 Day 56 (±3 days)	Day 84 (-7 days)	Week 12 Day 84 (±3 days)	Week 14 Day 98 (±3 days)	
Pharmacokinetic nintedanib/pirfenidone sample plasma x 2 (predose and at least 2 hours post dose to PLN-74809) ⁱ			X		X			X		X ^{e,f,h}
Pharmacogenomic sample			X							
Plasma biomarker samples			X		X			X		
Serum biomarker samples			X		X			X		
Urine biomarker samples			X		X			X		
Urine pregnancy test (positive tests will be confirmed with a serum test)			X		X	X		X		X
Urinalysis (dipstick, followed up by micro if abnormal)	X		X		X	X				X
Adverse events				↔						
Concomitant medications				↔						
Study drug administration (empty stomach: 2 hours predose and 2 hours postdose) ^j				↔						
Study drug dispensing			X		X	X				
Study drug accountability					X	X		X		X

DL_{CO} = diffusing capacity for carbon monoxide; ECG = electrocardiogram; EoS = end of study; ET = early termination; FEV1 = forced expiratory volume during the first seconds of the forced breath; FVC = forced vital capacity; MRI = magnetic resonance imaging; PET = positron emission tomography; PK = pharmacokinetic; VAS = visual analog scale

^a Visits 7 and 8 may be combined.

^b Baseline FVC to be obtained both during screening and on Day 1.

^c A historical value may be used if it has been completed within 1 month from the Baseline visit.

^d When time points for ECGs, vital sign assessment, and blood draws coincide, procedures should be carried out with blood draws last. ECGs should be collected postdose and close to the time of PK sample collection with the triplicate ECGs recorded within ~ 5 to 10 minutes. The triplicate ECGs will be averaged, and the mean values per time point (average of the 3 assessments) used to interpret the ECG tracings.

^e ECG abnormality, then PK sample will be collected.

	Screening	Treatment							EoS / ET
	Visit 1	Visit 2	Visit 3	Visit 4	Visit 5	Visit 6	Visit 7 ^a	Visit 8 ^a	Visit 9
	Day -28 to Day -1	Pre- Baseline Day -7 to Day -1	Baseline Day 1	Week 2 Day 14 (±2 days)	Week 4 Day 28 (±2 days)	Week 8 Day 56 (±3 days)	Day 84 (-7 days)	Week 12 Day 84 (±3 days)	Week 14 Day 98 (±3 days)

^f Liver function test abnormality, then PK sample will be collected.

^g Total and unbound PLN-74809 levels will be measured at the following timepoints:

Day 1: predose and 2, 4, and 6 hours postdose

Weeks 4 and 12: predose and at least 2 hours postdose

Actual PK sample collection time and dosing time will be recorded.

^h If the participant discontinues the study early, a plasma sample for PK should be taken at the ET Visit if possible.

ⁱ For participants receiving nintedanib/pirfenidone only; timed relative to PLN-74809 dosing.

^j Participants should be instructed to take study drug in the clinic on Visits 3, 5 and 8, and at the ET visit if applicable.

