3 INVESTIGATIONAL PLAN

3.1 Overall Study Design and Plan

This is a Phase 2a, single-center, randomized, double-blinded, placebo-controlled study to evaluate type 1 collagen deposition in the lungs following once-daily (QD) treatment with 160 mg PLN-74809 for 12 weeks in participants with IPF.

The study consists of an up to 28-day screening period, a 12-week treatment period, and a 2-week (± 3 days) post treatment follow-up period.

Potential participants who provide written informed consent will be screened for study eligibility up to 28 days before administration of the first dose of study drug. Approximately 12 eligible participants will be randomized in a 2:1 ratio (160 mg PLN-74809 vs placebo; 8 receiving PLN-74809 and 4 receiving placebo) on Day 1 (Visit 3). Study treatment will be administered once daily for 12 weeks. Randomization will be stratified by use of standard of care (SoC) IPF therapy with pirfenidone or nintedanib (SoC use; yes or no).

^{68}Ga -CBP8 PET/MRI scans will be conducted within 7 days prior to baseline and at or within 7 days prior to Week 12, as indicated in the Schedule of Events ([Appendix 1](#)).

Participants who discontinue study drug for safety reasons prior to completion of 12 weeks of treatment will be encouraged to remain in the study to complete all remaining assessments; if this is not feasible, they will be asked to return to the clinic for an Early Termination (ET) visit for follow-up evaluations. If a participant elects to withdraw from the study after the 6th week of randomization, an end of participation ^{68}Ga -CBP8 PET/MRI will be offered to the participant to enhance appropriate data capture.

Potential acute exacerbations, respiratory-related hospitalizations, and/or respiratory-related deaths will be reviewed by an adjudication committee.

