18. Any of the following liver function test criteria above specified limits: total bilirubin $> 1.5 \times$ the upper limit of normal (ULN); aspartate aminotransferase (AST) or alanine aminotransferase (ALT) $> 3 \times$ ULN; alkaline phosphatase $> 2.5 \times$ ULN.

Note: participants currently receiving nintedanib or pirfenidone as IPF SoC treatment, who have previously presented any liver function test elevations associated with nintedanib or pirfenidone treatment greater than that described above or resulting in dose reduction, treatment interruption, or discontinuation are not eligible.
19. Any of the following at screening: hemoglobin < 10.0 g/dL, neutrophils < 1500 /mm³, or platelets $< 100,000$ /mL
20. Electrical implants such as cardiac pacemaker or perfusion pump
21. Ferromagnetic implants such as aneurysm clips, surgical clips, prostheses, artificial hearts, valves with steel parts, metal fragments, shrapnel, metallic tattoos anywhere on the body, tattoos near the eye, or steel implants, ferromagnetic objects such as jewelry or metal clips in clothing
22. Claustrophobic reactions
23. Research-related radiation exposure exceeds current Radiology Department guidelines (i.e. 50 mSv in the prior 12 months)
24. Unable to lie comfortably on a bed inside the PET/MRI
25. Body mass index (BMI) > 33 kg/m² (limit of the PET/MRI table)
26. Prior or current radiation to the thorax
27. Pregnant or lactating female participants
28. Male participants with pregnant female partners
29. A medical or surgical condition known to affect drug absorption (e.g., major gastric surgery)
30. Participation in a clinical study with an investigational agent in the 30 days prior to screening or 5 half-lives of the investigational drug, whichever is longer trial, apart from PLN-74809
31. Currently receiving and expected to remain on treatment during the study with: potent and concomitant inhibitors or inducers of cytochrome P450 (CYP) 3A4, 2C9 or 2C19; potent inhibitors or inducers of P-glycoprotein (P-gp), breast cancer resistance protein (BCRP) or organic anion transporting polypeptide (OATP) 1B1/1B3 transporters; digoxin (a P-gp substrate with a narrow therapeutic window)

32. Daily use of phosphodiesterase-5 (PDE-5) inhibitor drugs (e.g., sildenafil, tadalafil, other) (Note: Intermittent use for erectile dysfunction is allowed.)
33. Surgical procedures planned to occur during the study period
34. Uncontrolled systemic arterial hypertension

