6.7.4 Contraception

Female Participants of Childbearing Potential

Female participants of childbearing potential must agree to use a contraceptive method with a failure rate of <1% per year or remain abstinent (refrain from heterosexual intercourse, if that is their preferred and established lifestyle) during the treatment period and for 1 month after the last dose of study treatment.

A woman is considered to be of childbearing potential if:

- She has not reached a postmenopausal state, defined as ≥ 12 continuous months of amenorrhea with no identified cause other than menopause or 6 months of spontaneous amenorrhea with serum follicle-stimulating hormone [FSH] levels >40 mIU/mL
- She has not undergone surgical sterilization, defined as hysterectomy, bilateral salpingectomy, and/or bilateral oophorectomy

Examples of contraceptive methods with a failure rate of < 1% per year include:

- Bilateral tubal ligation
- Male sterilization (>3 months from Day 1 or provide a zero sperm count)
- Hormonal contraceptives that inhibit ovulation (initiated >3 months from Day 1)
- Hormone-releasing intrauterine devices (initiated >3 months from Day 1)
- Copper intrauterine devices (initiated >3 months from Day 1)

Male Participants

Male participants, including those who are surgically sterile, must agree to use contraceptive measures, as defined below, or alternately to remain abstinent (refrain from heterosexual intercourse)

- Male participants, with female partners of childbearing potential, must use a condom plus an additional contraceptive method that together result in a failure rate of < 1% per year or remain abstinent during the treatment period and for at least 3 months after the last dose of study treatment.
- Male participants with pregnant female partners are excluded from this study.
- Male participants whose female partners become pregnant during the study must stop the medication immediately as outlined in [Section 8.6](#).

Female and Male Participants

Highly effective methods of birth control are defined as those with a failure rate of < 1% per year (adapted from [Trussell, 2004](#); [CTFG 2014](#)).

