7.10 Pharmacodynamic Assessments

7.10.1 PET/MRI Imaging for the Assessment of Type 1 Collagen Deposition

All PET/MRI will be performed at the Martinos Center for Biomedical Imaging at Massachusetts General Hospital. PET imaging will be performed at prespecified times according to the Schedule of Events ([Appendix 1](#)) using the collagen-targeted tracer, ⁶⁸Ga-CBP8 as synthesized at the Martinos Center for Biomedical Imaging, and following predefined instructions as detailed in the Radiology Manual for the study. The radiochemical dose is up to 12.9 mCi per administration; but in practice, the dose averages to 5.5 mCi per subject. The total amount of radiation exposure from the PET/MRI is equal to a whole-body exposure up to 22 mSv (11 mSv per administration of ⁶⁸GaCBP8). Blood samples will be obtained prior to each PET/MRI and will be stored for future analyses. Details for blood sample collection and processing are detailed in the Radiology Manual.

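### No pregnancy test or eligibility check is scheduled at the baseline scan visit, so the last result may be up to 27 days old when tracer and contrast are given

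*Protocol*

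**What the plan says.** Exclusion 27 in Protocol 4.3 reads "Pregnant or lactating female participants". Women of childbearing potential are nonetheless expressly admitted by inclusion 8, subject to contraception.

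On timing, Protocol 3.1 has participants "screened for study eligibility up to 28 days before administration of the first dose of study drug" and states that "PET/MRI scans will be conducted within 7 days prior to baseline and at or within 7 days prior to Week 12". Appendix 1 then sets out:

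- "Serum pregnancy test": Visit 1 only (Day -28 to -1).
- "Urine pregnancy test (positive tests will be confirmed with a serum test": Visit 3 (Day 1), Week 4, Week 8, Week 12 (Visit 8) and the end-of-study or early-termination visit.
- Inclusion and exclusion check: Visits 1 and 3.
- PET/MRI: Visit 2 (Day -7 to -1), and a second mark that the extracted table shows under Visit 8. Visit 7 (Day 84, minus 7 days) carries no marks in that table. Footnote a lets Visits 7 and 8 be combined.

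On exposure, Protocol 7.10.1 says "The total amount of radiation exposure from the PET/MRI is equal to a whole-body exposure up to 22 mSv", made up of 11 mSv per administration. Section 7.10.2 adds gadoterate at every session.

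The contraception period for women in 6.7.4 (and inclusion 8) is "during the treatment period and for 1 month after the last dose of study treatment".

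**The concern.** The check for an exclusion should come before the exposure that the exclusion guards against. At Visit 2 the schedule relies on a result that may be several weeks old, and the next scheduled test falls after the scan. The stated contraception period starts with treatment, so it does not explicitly cover the screening weeks that contain the first scan.

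What is at stake is avoidable fetal exposure to radiation and gadolinium contrast. There is also a lesser loss: randomization is on Day 1, so a participant found pregnant that day has used a baseline scan and cannot be randomized. The analysis of the primary endpoint is not affected.

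**Working it through.** No sample-size or power figure bears on this. The check is day arithmetic on the visit windows in Appendix 1. The SAP's study-day definition (5.2.9) has no Day 0, so Day -1 is the day before Day 1.

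**Baseline scan**

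1. Age of the screening serum result at the scan. Earliest test Day -28, latest scan Day -1: -1 - (-28) = 27 days. The Visit 1 and Visit 2 windows overlap from Day -7 to Day -1, so the minimum is 0 days, and no order is stated for that case. Range: 0 to 27 days.
2. Scan to the first urine test on Day 1. A scan on Day -1 is 1 day before Day 1, and a scan on Day -7 is 7 days before. Range: 1 to 7 days, with the scan always first.
3. Exposure at that scan: 22 mSv / 2 administrations = 11 mSv at most, plus gadoterate.
4. Does other protocol text fill the gap? Blood is drawn before each PET/MRI (7.10.1), but it is described as stored for later analysis, not as a pregnancy test. Eligibility is rechecked at Visit 3, not at Visit 2.

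**Second scan**

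5. Week 8 urine test: Day 56 ± 3 = Day 53 to 59. Visit 7 window: Day 84 - 7 = Day 77 to Day 84.
6. Shortest gap: 77 - 59 = 18 days. Longest: 84 - 53 = 31 days. This applies only if the scan is done before Visit 8.
7. If the 7 days are counted back from the actual Week 12 visit (Day 81 to 87), the scan could fall on Day 74 to 87. The range is then 74 - 59 = 15 to 87 - 53 = 34 days. A scan on Day 87 would be on the Week 12 visit day itself, when a urine test is also due.
8. If the scan is at Visit 8, or at a combined Visit 7/8, a urine test falls at the same visit. The schedule does not say which comes first.

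**The case against.** A reader might infer that no pregnancy test precedes either scan. The documents do not support that. The serum test belongs to screening and normally precedes the baseline scan, so a pregnancy detectable then would ordinarily be caught. Urine tests on Day 1, Week 4 and Week 8 all precede the second scan. What remains is a pregnancy conceived after the screening test or too early for it to detect.

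A reader might also infer that nothing requires contraception during screening. That goes too far. Among the example methods in 6.7.4, hormonal methods and intrauterine devices must have been started more than 3 months from Day 1. Male sterilization carries the same lead time or a zero sperm count. Tubal ligation is permanent, and abstinence is tied to an established lifestyle. Much of the screening interval is thus covered in substance. The remaining point is narrower: the list gives examples, and the stated period does not name screening.

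The second-scan limb is weak. The extracted table prints that scan under Visit 8, alongside a urine test, and column positions may be disturbed by extraction. The gap of 18 to 31 days arises only under the text's 7-day window.

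Finally, sections 7.10.1 and 7.10.2 defer scan conduct to the Radiology Manual, where a pre-injection check could sit. This objection stands as a limit on certainty: the protocol is silent, which does not show that no check exists. It does not remove the point, because no protocol passage refers to such a check and Appendix 1 is where the other pregnancy tests are scheduled.

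**Conclusion.** The point holds for the baseline scan. As scheduled, tracer and gadoterate are given at a visit with no pregnancy test and no eligibility check, on a serum result up to 27 days old and 1 to 7 days before the next test. A participant barred by exclusion 27 could receive up to 11 mSv and contrast before the pregnancy is found.

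For the second scan the point is secondary: a last test 18 to 31 days old if the scan precedes Visit 8, or an unstated order if test and scan share a visit.

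This rests on reading Appendix 1 as extracted and on the Radiology Manual containing no overriding check, which cannot be verified here. The probability is low. The trial plans about 12 participants aged 40 or over, and the documents do not say how many will be women of childbearing potential; there may be none. Because the harm is avoidable and the correction is cheap, the schedule should still be changed.

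**What to change.** Reconcile exclusion 27, section 6.7.4, sections 7.10.1 and 7.10.2, and Appendix 1, so that:

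- the schedule documents pregnancy status before each tracer administration, including where Visits 7 and 8 are combined;
- the stated contraception period (inclusion 8 and 6.7.4) is consistent with the date of the first scan;
- if the Radiology Manual already holds a pre-scan check, Appendix 1 refers to it.

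The type of test and its timing are for the sponsor and investigator to decide. The cost is about one extra or retimed urine test per woman of childbearing potential and a schedule footnote. No analysis changes.
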